6.3.1 Cytokine Release Syndrome (CRS)

Cytokine release syndrome is clinically defined and may have various manifestations. Most cancer immunotherapies bear the risk of cytokine-associated toxicity, also known as cytokine release syndrome caused by non-antigen specific high level immune activation ([Lee et al, 2014](#) and [Appendix E](#)). Signs and symptoms of CRS may include:

- Constitutional – fever, rigors, fatigue, malaise
- Neurologic – headache, mental status changes, dysphasia, tremors, dysmetria, gait abnormalities, seizure
- Respiratory – dyspnea, tachypnea, hypoxemia
- Cardiovascular – tachycardia, hypotension
- Gastrointestinal – nausea, vomiting, transaminitis, hyperbilirubinemia
- Hematology – bleeding, hypofibrinogenemia, elevated D-dimer
- Skin – rash

Subjects may be at an increased risk for cytokine release syndrome during the first few days following the initial infusion of AMG 596 and/or AMG 404. Cytokine release syndrome may be life-threatening or fatal. Infusion reactions may be clinically indistinguishable from manifestations of cytokine release syndrome. Throughout the infusion with AMG 596 and/or AMG 404, monitor subjects for clinical signs (eg, fever, tachycardia, dyspnea, tremors) and laboratory changes (eg, transaminase increase) which may be related to cytokine release syndrome. In the event of CRS, an unscheduled blood sample should be collected to measure cytokine levels.

Grading of cytokine release syndrome should be performed according to the recommendations provided by [Lee et al, 2014](#). (see [Section 13](#) and [Appendix E](#)).

Interventions for cytokine release syndrome will be determined by its particular manifestations and magnitude in each subject. Pyrexia may be managed with paracetamol/acetaminophen. Management of hypotension should be managed by volume resuscitation and, in the event that it is not sufficient or if there is evidence of volume overload, pressor support may be added, with the type of vasopressive agent determined by the investigator depending on the totality of observed hemodynamic parameters (heart rate, cardiac output, central venous pressure).

For grade 2 CRS, the study drug should be interrupted and monitoring and management of CRS symptoms should be performed as described above and according to published recommendations by [Lee et al, 2014 \(Appendix E\)](#). The study drug should be permanently discontinued for grade 2 CRS not improving to grade ≤ 1 within 7 days ([Appendix E](#)).

For grade 3 or greater cytokine release syndrome, the study drug should be interrupted and immunosuppressive therapies should be provided. Corticosteroids such as dexamethasone or methylprednisolone are the preferred choice for immunosuppression. Typical doses for dexamethasone are 8 mg IV q8 hours with subsequent tapering following symptom resolution. Tocilizumab has been reported to be efficacious in this setting at a dose of 4-8 mg/kg as a single dose. However, due to the reported potential aggravation of IL-6 levels in CNS in association with tocilizumab treatment decision should include careful risk-benefit evaluation. The study drug should be discontinued for grade 3 CRS not improving to grade ≤ 2 within 5 days or grade ≤ 1 within 7 days ([Appendix E](#)).

For grade 4 cytokine release syndrome, the study drug should be interrupted immediately and permanently discontinued. The subject should be transferred to an intensive care unit ([Appendix E](#)). After observation of first DLT (in DLT period 1) associated to cytokine release-associated adverse events, step dosing and/or prophylactic treatment with steroids (dexamethasone) is recommended to mitigate the cytokine release syndrome risk in further subjects.

Prophylactic dexamethasone treatment according to the following schema will be recommended to all subject after the observation of a first cytokine release syndrome of grade 2 (see [Appendix E](#)) or higher.

- Dexamethasone at a dose of 4 to 8 mg or equivalent corticosteroid will be administered orally or IV
 - 8 to 12 hours prior to the start of the infusion on day -1
 - 1 hour prior to the start of the infusion on day 1
 - Every 8 to 12 hours after start of infusion for first 24 hours of the infusion
- Corticosteroid treatment can be continued if deemed necessary by the investigator and after consultation with the sponsor but doses should be tapered as quickly as feasible. Close monitoring of blood glucose levels is recommended in such a case. Further variations may be needed that should be discussed and agreed upon in a DLRM.

Approved

6.3.2 Infusion Interruption/Dose Modification due to Neurologic Events

Patients with glioblastoma or malignant glioma may present with generalized symptoms (eg, headaches, cognition and personality changes) and focal signs (eg, hemiparesis, sensory loss, visual field disturbances) (Omuro and DeAngelis, 2013).

Recommendations for management, including interventions and infusion interruptions for neurologic-related adverse events, are presented in Table 5. As neurologic events may be anticipated in the study population, guidance regarding reporting of safety events, including disease-related and adverse events, is provided in Section 9 (Safety Data Collection, Recording, and Reporting).

Table 5. Management of Neurologic Events (by Severity)

| CTCAE Grade | Intervention | Instructions for Infusion Interruption or Permanent Discontinuation |
|-------------|--|---|
| 3 | 
Perform physical exam, assess vital signs and conduct safety laboratory tests
 
Depending on the nature of the adverse event, additional measures (eg, CSF investigations, contrast-enhanced MRI of the head) can be taken upon discretion of the investigator
 
MRI should also be considered for subjects who permanently discontinue treatment at the discretion of investigator
 | 
Immediately interrupt AMG 596
 
Restart AMG 596 infusion within 2 weeks, but not earlier than 72 hours (3 days) after the infusion has stopped, if the event resolves to grade ≤ 1 within 7 days
 
Delay AMG 404 dosing until day 8 after AMG 596 restart if AMG 404 dosing was scheduled during interruption
 
Permanently discontinue AMG 596 and AMG 404 if considered by the investigator related to study drug and if there is no improvement to grade ≤ 1 within 7 days
 |
| 4 | 
Perform physical exam, assess vital signs and conduct safety laboratory tests
 
Depending on the nature of the adverse event, additional measures (eg, CSF investigations, contrast-enhanced MRI of the head) can be taken upon discretion of the investigator
 
Conduct MRI for subjects who permanently discontinue treatment
 | 
Immediately interrupt AMG 596
 
Permanently discontinue AMG 596 and AMG 404
 |

CSF – cerebrospinal fluid, CTCAE – Common Terminology Criteria for Adverse Events, MRI – magnetic resonance imaging

For subjects who experience serious neurologic adverse events leading to treatment interruption, if the event has decreased to at least CTCAE grade 1 within 1 week,

Approved

treatment may be restarted within 2 weeks, but not earlier than 72 hours (3 days) after the infusion was stopped.

Seizure

If the neurologic event was a seizure (CTCAE grade 2 or above), appropriate prophylactic anticonvulsant treatment (a therapeutic dose of eg, phenytoin or levetiracetam) can be administered during the next treatment cycle. In case of occurrence of seizure grade 3, the investigational products will have to be stopped immediately and treatment will be permanently discontinued, and investigations associated with and previously described for a CTCAE grade 3 or higher neurologic-related adverse events, must also be performed.

Depressed level of consciousness

Depressed level of consciousness is a common neurological sign of intracranial pressure increase. AMG 596 may cause inflammation at the site of the tumor, leading to worsening of increased intracranial pressure resulting in neurological toxicity including a depressed level of consciousness.

Prophylactic use of corticosteroids is mandated for any subject receiving a new cycle of AMG 596 (████████████████████), with dexamethasone 8 mg IV (or equivalent dose of other corticosteroids) given within 1 hour prior to administration of AMG 596 and the second dose of dexamethasone 8 mg IV given 12 hours after start of the infusion, and subsequent tapering at the discretion of the investigator. Prophylactic treatment with steroid (eg, dexamethasone) is also mandated before restarting of AMG 596 or otherwise clinically indicated (see [Section 6.3](#)).

6.3.3 Hepatotoxicity Stopping and Rechallenge Rules

Subjects with abnormal hepatic laboratory values (ie, ALP, AST, ALT, TBL) and/or international normalized ratio (INR) and/or signs/symptoms of hepatitis (as described below) may meet the criteria for withholding or permanent discontinuation of Amgen investigational product or other protocol-required therapies as specified in the Guidance for Industry Drug-Induced Liver Injury: Premarketing Clinical Evaluation, July 2009.

Approved

6.3.4 Criteria for Permanent Withholding of Amgen Investigational Product due to Potential Hepatotoxicity

Both investigational products should be discontinued permanently, and the subject should be followed according to the recommendations in [Appendix A](#) (Additional Safety Assessment Information) for possible drug-induced liver injury (DILI), if ALL of the criteria below are met:

- TBL > 2 × ULN or INR > 1.5
- AND increased AST or ALT from the relevant baseline value as specified below:
 - Baseline AST or ALT value: < ULN
 - AST or ALT elevation: > 3 × ULN
- AND no other cause for the combination of the above laboratory abnormalities is immediately apparent; important alternative causes for elevated AST/ALT and/or TBL values include, but are not limited to:
 - Hepatobiliary tract disease
 - Viral hepatitis (eg, Hepatitis A/B/C/D/E, Epstein-Barr Virus, cytomegalovirus, Herpes Simplex Virus, Varicella, toxoplasmosis, and Parvovirus)
 - Right sided heart failure, hypotension, or any cause of hypoxia to the liver causing ischemia
 - Exposure to hepatotoxic agents/drugs or hepatotoxins, including herbal and dietary supplements, plants, and mushrooms
 - Heritable disorders causing impaired glucuronidation (eg, Gilbert's Syndrome, Crigler-Najjar syndrome) and drugs that inhibit bilirubin glucuronidation (eg, indinavir, atazanavir)
 - Alpha-one antitrypsin deficiency
 - Alcoholic hepatitis
 - Autoimmune hepatitis
 - Wilson's disease and hemochromatosis
 - Nonalcoholic Fatty Liver Disease including steatohepatitis (NASH)
 - Non-hepatic causes (eg, rhabdomyolysis, hemolysis)

If an alternative cause for hepatotoxicity is identified or less stringent conditions developed than what are noted above, determine (based on patient population and/or severity of the hepatotoxicity or event) if Amgen IP and other protocol-required therapies should be withheld or permanently discontinued, as deemed appropriate for the safety of the subject.

Approved

6.3.5 Criteria for Conditional Withholding of Amgen Investigational Products due to Potential Hepatotoxicity

For subjects who do not meet the criteria for permanent discontinuation of Amgen investigational products outlined above and have no underlying liver disease, and eligibility criteria requiring normal transaminases and TBL at baseline or subjects with underlying liver disease and baseline abnormal transaminases, the following rules are recommended for withholding of Amgen investigational products and other protocol required therapies:

- Elevation of either AST or ALT according to the following schedule:
 - Baseline AST or ALT value: Any AST or ALT elevation: $> 8 \times \text{ULN}$ at any time
 - Baseline AST or ALT value: Any AST or ALT elevation: $> 5 \times \text{ULN}$ but $< 8 \times \text{ULN}$ for ≥ 2 weeks
 - Baseline AST or ALT value: Any AST or ALT elevation: $> 5 \times \text{ULN}$ but $< 8 \times \text{ULN}$ and unable to adhere to enhanced monitoring schedule
 - Baseline AST or ALT value: Any AST or ALT elevation: $> 3 \times \text{ULN}$ with clinical signs or symptoms which are consistent with hepatitis (such as right upper quadrant pain/tenderness, fever, nausea, vomiting, or jaundice).
- OR: TBL $> 3 \times \text{ULN}$ at any time
- OR: ALP $> 8 \times \text{ULN}$ at any time

For transaminitis of CTCAE grade 3 or 4 suspected to be caused by cytokine release infusion interruption and discontinuation criteria should apply as defined in [Appendix E](#).

AMG 596 and AMG 404 should be withheld pending investigation into alternative causes of DILI. If the investigational product is withheld, the subject is to be followed according to recommendations in [Appendix A](#) for possible DILI. Rechallenge may be considered if an alternative cause for impaired liver tests (ALT, AST, ALP) and/or elevated TBL is discovered and the laboratory abnormalities resolve to normal or baseline (see [Section 6.3.3](#) and [Section 6.3.6](#).)

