111. Renal function as follows: serum creatinine < 2.0 mg/dL and estimated glomerular filtration rate ≥ 60 mL/min/1.73 m² by MDRD and urine protein quantitative value of < 30 mg/dL in urinalysis or $\leq 1+$ on dipstick

Approved

112. Hepatic function as follows:
- Aspartate aminotransferase (AST) and Alanine aminotransferase (ALT) ≤ 3.0 x upper limit of normal (ULN)
 - Bilirubin ≤ 1.5 x ULN (unless considered due to Gilbert's syndrome or hemolysis)

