6.3.6 Criteria for Rechallenge of Amgen Investigational Product After Potential Hepatotoxicity

The decision to rechallenge the subject should be discussed and agreed upon unanimously by the subject and investigator, after consultation with Sponsor.

If signs or symptoms recur with rechallenge, then the investigational products should be permanently discontinued. Subjects who clearly meet the criteria for permanent discontinuation (as described in [Section 6.2.5](#)) should never be rechallenged.

Approved

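### The combined liver-injury stopping rule in 6.3.4 covers only a normal baseline, so eligible subjects with both AST and ALT at or above ULN can never meet it

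*Protocol*

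**What the plan says.** - **Eligibility (Protocol 4.1, criterion 112).** Hepatic function must satisfy "Aspartate aminotransferase (AST) and Alanine aminotransferase (ALT) ≤ 3.0 x upper limit of normal (ULN". Baseline values from 1.0 to 3.0 x ULN are therefore allowed for both enzymes.
- **Permanent stop (6.3.4).** "Both investigational products should be discontinued permanently" if every listed criterion is met: TBL > 2 x ULN or INR > 1.5; a rise in AST or ALT from the relevant baseline; and no other immediately apparent cause. The single baseline category is "Baseline AST or ALT value: < ULN", paired with an on-study value > 3 x ULN.
- **Fallback (end of 6.3.4).** If another cause is found, or "less stringent conditions developed than what are noted above", the decision to withhold or discontinue is made case by case, with no threshold.
- **Conditional hold (6.3.5).** The enzyme lines apply to any baseline: > 8 x ULN; > 5 to < 8 x ULN for at least 2 weeks, or when enhanced monitoring cannot be followed; or > 3 x ULN with signs or symptoms of hepatitis. TBL > 3 x ULN or ALP > 8 x ULN also triggers a hold. No line uses INR. The preamble names two populations: subjects without liver disease under "eligibility criteria requiring normal transaminases and TBL at baseline", "or subjects with underlying liver disease and baseline abnormal transaminases".
- **Appendix A.** The specific 24-hour DILI report refers back to the 6.3 criteria. Close observation starts at > 3 x ULN or at a 2-fold rise over a raised baseline, with retesting every 24 hours when TBL > 2 x ULN or INR > 1.5.

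**The concern.** The wording of 6.3.4 implies several baseline categories but gives one, and that one is narrower than eligibility. Two subjects with the same on-study transaminases, bilirubin and INR, and no other cause, are handled differently. With normal enzymes at entry, both products should be stopped for good and the event reported within 24 hours. With both enzymes mildly raised at entry, the decision is individual judgement and the specific report is not called for.

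Safety is the primary endpoint, the combination had no clinical safety data when the amendment was written (2.5.3.2), and AMG 596 raised ALT and/or AST in monkeys (2.2.3). A combined transaminase plus TBL/INR stop should work for everyone the protocol enrolls.

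**Working it through.** The plan gives no figure to reproduce. The check sets the rules side by side and then tests the proposed wording.

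**1. Who can meet 6.3.4?** Take baseline AST and ALT each at 0.5, 0.9, 1.0, 1.5, 2.0, 2.5 or 3.0 x ULN: 49 eligible pairs. Let on-study enzymes rise without limit, with TBL and INR above their limits and no other cause.

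| Baseline | Pairs | Can meet 6.3.4 |
|---|---|---|
| Both < ULN | 4 | 4 |
| One < ULN | 20 | 20 |
| Both >= ULN | 25 | 0 |

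The result is the same whether AST or ALT is read enzyme by enzyme or loosely. The zero follows directly from the text. In 9 of the 25 pairs an enzyme sits at exactly 1.0 x ULN, a boundary case; the other 16 have both enzymes clearly raised.

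**2. Does 6.3.5 catch the event instead?** Take AST/ALT > 3 to 5 x ULN, TBL > 2 to 3 x ULN or INR > 1.5, no symptoms, ALP not > 8 x ULN.
- > 8 x ULN, or > 5 x ULN with duration or monitoring failure: not met.
- > 3 x ULN with symptoms: not met.
- TBL > 3 x ULN: not met. ALP > 8 x ULN: not met. INR: no line.

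On a grid of 25 baseline pairs x 16 on-study pairs (each enzyme 3.5, 4.0, 4.5 or 5.0 x ULN) x 2 (TBL 2.5 x ULN, or INR 1.7) = 800 combinations, 6.3.4 is met in 0 and 6.3.5 in 0.

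**3. What would a raised-baseline row do?** The threshold per enzyme is max(3 x ULN, k x baseline).

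| Baseline (x ULN) | 1.0 | 1.5 | 2.0 | 2.5 | 3.0 |
|---|---|---|---|---|---|
| k = 2 | 3 | 3 | 4 | 5 | 6 |
| k = 1.5 | 3 | 3 | 3 | 3.75 | 4.5 |

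For k = 2, one enzyme passes at 4 + 4 + 3 + 1 + 0 = 12 of its 20 baseline/on-study combinations and fails at 8. Both fail in 8 x 8 = 64 of 400, so the row is met in (400 - 64) x 2 = 672 of 800. For k = 1.5, an enzyme fails at 3 of 20, so the row is met in (400 - 9) x 2 = 782 of 800.

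**4. Worked cases.** Case A: AST 4.0, ALT 4.5, TBL 2.5 x ULN. Case B: same enzymes, TBL 1.2 x ULN, INR 1.7. As written, 0 of 25 pairs meet 6.3.4. With k = 2, 21 of 25 do; the 4 missed have both baselines at 2.5 or 3.0 x ULN. With k = 1.5, 25 of 25 do. Leaving out the 9 boundary pairs, k = 2 gives 12 of 16 and k = 1.5 gives 16 of 16.

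These counts show how the wording behaves. They are not frequencies.

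**The case against.** The strongest reply is that the window is small and supervised. It requires both enzymes raised at entry, no symptoms (fever, nausea, vomiting and jaundice all count), no cytokine release, no other cause, TBL not above 3 x ULN and ALP not above 8 x ULN. Inside it, close observation is mandatory, and the case-by-case sentence in 6.3.4 permits a permanent stop. Table 4 delays the infusion at grade 3 and stops it at grade 4, the DLT rule in 6.2.5 applies, and 9.1.3 lets the investigator classify liver injury as medically important. For a subject who enters at 3.0 x ULN, an automatic permanent stop just above 3 x ULN would be unreasonable, so some judgement is defensible. All of this stands, and it limits the size of the point.

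A reader might infer that these subjects have no liver stopping rule. The documents do not support that: the 6.3.5 enzyme lines apply at any baseline, "For transaminitis of CTCAE grade 3 or 4 suspected to be caused by cytokine release" is routed to Appendix E, and 6.3.6 states "If signs or symptoms recur with rechallenge, then the investigational products should be permanently discontinued". Nor does one raised enzyme disable 6.3.4; both must be raised.

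A reader might also infer that in Arm 2 the Appendix G grade 2 hepatitis hold on AMG 404 is lost. That goes too far. Its bilirubin limb is joined by and/or, and the normal-baseline condition can be read per analyte. If baseline TBL is below ULN, AMG 404 may still be held. The hold is not clear through the enzyme limb, and there is none for an INR-only event.

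Two limits remain. Section 6.3.3 points to an outside guidance whose content cannot be checked here. The protocol also prints no CTCAE liver bands for a raised baseline and no INR grade, so the Table 4 row that applies is open.

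**Conclusion.** The point holds, and it should be fixed. For eligible subjects with both AST and ALT at or above ULN, the only combined transaminase plus TBL/INR permanent stop cannot be met. In the window above, no 6.3.5 hold line applies, and the Appendix A 24-hour report tied to 6.3 is not triggered. An explicit rule, itself worded as a recommendation, is replaced by individual judgement, Table 4 grading, the DLT rule, general serious adverse event reporting and close observation.

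The conclusion assumes that no row of 6.3.4 was lost from the text, which is unlikely because the surrounding bullets are intact. The documents do not give the share of subjects with both enzymes raised, so the practical frequency is unknown. The mismatch between the 6.3.5 preamble and criterion 112 is editorial, because every enzyme line there already covers any baseline.

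**What to change.** 1. **6.3.4:** add a row for baseline AST/ALT >= ULN with a baseline-relative rise, for example on-study > 3 x ULN and at least 2 x baseline, combined with TBL > 2 x ULN or INR > 1.5. Appendix A already uses a 2-fold rise for close observation. The sponsor should confirm the multiplier.
2. **6.3.5:** add a hold line for AST/ALT > 3 x ULN with TBL > 2 x ULN or INR > 1.5 at any baseline. On the grid above, this turns the 800 - 672 = 128 combinations missed by the 2 x row into holds.
3. **6.3.5 preamble:** align it with criterion 112 as an editorial change.
4. **Appendix G, grade 2 hepatitis (optional):** state that the normal-baseline condition applies per analyte, and add an enzyme threshold for a raised baseline.

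The cost is amendment wording. Liver tests and INR are already scheduled. The downside is that a few more subjects may be held or taken off treatment.

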6.2.4 Dosage Adjustments, Delays, Rules for Withholding or Restarting, Permanent Discontinuation

6.2.4.1 AMG 596

Dose Delay or Dose Reduction

Any clinically relevant (as determined by the investigator) grade 4 adverse event related to IP that does not meet the DLT criteria should lead to a dose delay and/or a dose reduction. The decision if a dose delay or reduction will be performed is up to the investigator's discretion. The sponsor may be consulted.

In addition, cytokine release syndrome of \geq grade 3 ([Appendix E](#)) should lead to dosing interruption and treatment with immunosuppressive therapies should be performed (see [Section 6.3](#) for details).

In case of re-appearance of the same grade 4 adverse event, IP should be permanently discontinued.

For persistent or re-occurring clinically relevant grade 3 adverse event related to IP, a dose delay or a dose reduction should be considered.

Infusion Interruption

Significant events requiring a change in treatment will be managed by immediate infusion interruption and should be documented in source documents and in the eCRF:

- The subject experiences a DLT as defined in [Section 6.2.3](#).
- The subject experiences a clinically relevant grade 4 adverse event related to IP (see above)
- The subject meets criteria for discontinuation of IP as described in [Section 8.3](#)
- Technical problem with the infusion pump
- The investigational product is incorrectly prepared or administered (eg, overdose)

Restarting the Infusion

Treatment may resume if the interruption is \leq 21 days:

- If the interruption occurred due to other reasons than toxicity (technical or logistic reasons; eg, diagnostic measurements). The infusion can be restarted at the same dose and without additional measures or delays.
- The toxicity has resolved to \leq grade 1. The infusion can be restarted according to guidelines presented in [Table 3](#) and [Table 4](#). Non-hematological Criteria for Dose Reduction.
- The toxicity occurred during the DLT period and has resolved to grade 2. The infusion can only be restarted in an individual subject with a clear clinical benefit from treatment after consultation with the sponsor on a case-by-case basis.

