| CTCAE Grade* | Dose Delay | Dose Reduction | Comment |
|---|-----------------------|---|---|
| Non-hematological | | | |
| Cytokine release syndrome, tumor lysis syndrome, acute kidney injury | | | |
| 2 | Delay until ≤ grade 1 | No change | Restart in hospital |
| 3 | Delay until ≤ grade 1 | Restart at 1 dose level lower | Consider re-escalation if completely recovered and no new toxicity occurred within 7 days of infusion. Permanent discontinuation of study treatment if no recovery within 21 days. Start at the same dose if resolved cytokine release syndrome, infection, tumor lysis syndrome, or hypoxia. |
| 4 | Discontinue infusion | Permanent discontinuation of study treatment | - |
| All other non-hematological toxicities and clinically significant laboratory parameters | | | |
| 0-2 | Continue infusion | No change | Interruption can be considered if deemed necessary by the investigator |
| 3 | Delay until ≤ grade 2 | Resolution to grade 1 or 2: Restart at 1 dose level lower Resolution to normal within 1 week or a relationship to study drug can be ruled out: No change | Per the Investigator medical discretion to decide whether to continue the infusion for up to 72 hours if the toxicity or abnormal labs are responding to treatment or represents an asymptomatic laboratory change. Permanent discontinuation of study treatment if no recovery within 21 days |
| 4 | Discontinue infusion | Permanent discontinuation of study treatment | - |

ANC = Absolute neutrophil count; CTCAE = Common terminology criteria for adverse events;

DLT = Dose-limiting toxicity

^a Applies to all hematologic toxicity that persists for > 24 hours despite appropriate treatment

* For CRS criteria defined in [Appendix E](#) apply

Approved

6.2.4.2 AMG 404

Dose Delay or Dose Reduction

Each subject will stay on the dose level assigned until treatment needs to be stopped. The reason for dose withholds and dose delays is to be recorded on each subject's CRF. Specific guidance for management of adverse events associated with AMG 404 are provided in [Appendix G](#)

Immune-related Adverse Reactions

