6.2.5 Permanent Discontinuation

A subject will permanently discontinue treatment with investigational products in the event of:

- Dose-limiting or other unmanageable toxicity. For exemption, please see [Section 6.2.3](#)).
- Clinically significant disease progression or deterioration.
- Occurrence of neurologic-related adverse event considered related to AMG 596 and/or AMG 404 by the investigator and meeting one or more of the following criteria:
 - Grade 3 seizure, ataxia or encephalopathy
 - A neurologic-related adverse event CTCAE grade 4
 - A neurologic-related adverse event leading to treatment interruption that needed more than 1 week to resolve to CTCAE grade ≤ 1
- Occurrence of acute kidney injury considered related to AMG 596 and/or AMG 404 by the investigator and meeting one or more of the following criteria:
 - Creatinine $> 3x$ baseline or > 4.0 mg/dL and not recovered to CTCAE grade 1 or ≤ 0.3 mg/dL within 21 days
 - Hemodialysis required
- Subject's request
- Subject or investigator not compliant with the study protocol
- Occurrence or progression of a medical condition which, in the opinion of the investigator after medical consideration, is not associated with the disease under study and should preclude further participation of the subject in the study
- Pregnancy
- A DLT leads to permanent discontinuation unless the following criteria apply, in which case a restart of treatment at the same or a lower dose may be allowed:
 - The AE (including relevant lab values) is reversible and improves to grade ≤ 1 or baseline within 14 days
 - The patient is experiencing clinical benefit as assessed by the investigator
 - There is agreement between the investigator and the Amgen Medical Monitor that treatment may be restarted
 - The subject is willing to continue treatment after the investigator has led an appropriate discussion of potential risks and benefits with the subject

All reasons for treatment discontinuation should be clearly and concisely documented in the eCRF. If a subject has not continued to present for study visits, the investigator should determine the reason and circumstances as completely and accurately as possible.

In any case of premature treatment discontinuation, the investigator should make every effort to perform all examinations scheduled for the end of treatment (EOT) and safety

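### Once a liver-test trigger in section 6.3.5 is met, Table 4 and sections 6.3.5/6.3.6 give different conditions for restarting AMG 596, and the protocol does not say which governs

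*Protocol*

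**What the plan says.** Three places in the current protocol bear on restarting AMG 596 after a raised AST or ALT.

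- **Table 4 (section 6.2.4.1), grade 3, residual row** for other non-hematological toxicities and significant laboratory changes. Treatment is delayed until grade 2 or lower. Then: "Resolution to grade 1 or 2: Restart at 1 dose level lower". Alternatively: "Resolution to normal within 1 week or a relationship to study drug can be ruled out: No change". Treatment stops for good if there is no recovery within 21 days.
- **Sections 6.3.5 and 6.3.6.** The 6.3.5 triggers include AST or ALT above 8 x ULN at any time; 5 to 8 x ULN for two weeks or more, or when enhanced monitoring cannot be followed; and above 3 x ULN with hepatitis symptoms. Once drug is withheld: "Rechallenge may be considered if an alternative cause for impaired liver tests (ALT, AST, ALP) and/or elevated TBL is discovered", with values back to normal or baseline. Section 6.3.6 adds: "The decision to rechallenge the subject should be discussed and agreed upon unanimously by the subject and investigator, after consultation with Sponsor".
- **Section 6.2.4.1, text on restarting.** Once the toxicity is grade 1 or lower, "The infusion can be restarted according to guidelines presented in" Tables 3 and 4. Recovery only to grade 2 is accepted for a toxicity in the DLT period, and then "The infusion can only be restarted in an individual subject with a clear clinical benefit from treatment after consultation with the sponsor".

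Two kinds of event are routed elsewhere. Transaminitis suspected to come from cytokine release goes to Appendix E, by a sentence in 6.3.5 and a footnote to Table 4. For DLTs, section 6.2.5 says: "A DLT leads to permanent discontinuation unless the following criteria apply".

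**The concern.** Two sites that each follow the text faithfully could make opposite decisions about re-exposing a subject after possible drug-induced liver injury. Table 4 looks only at how far the values have fallen. Section 6.3.5 asks first whether something other than the study drug explains the rise. A subject with no other explanation is the one for whom re-exposure carries most risk, and that is where the two rules part.

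The study is first-in-human and includes a combination for which section 2.5.3.2 expects adverse events from synergistic T-cell activation. Sponsor consultation does not close the gap, because it belongs to rechallenge under 6.3.6 and Table 4 does not require it.

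**Working it through.** The plan states no figure to reproduce, so the check applies each rule to the same subject.

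**Inputs and assumptions**
- Grade bands for AST/ALT come from the hepatitis rows of Appendix G: grade 2 is above 3 and up to 5 x ULN, grade 3 is 5 to 20 x ULN. Values above normal and up to 3 x ULN are taken as grade 1. The protocol does not reproduce the CTCAE cut-offs, so using these bands is an assumption.
- Baseline ALT is below ULN.
- The rise is clinically significant, not due to cytokine release, outside the DLT period and not declared a DLT.
- Bilirubin and INR do not meet the permanent-stop test in 6.3.4.
- No alternative cause is found, and a drug relationship is not ruled out.
- In case D the subject has no symptoms and is monitored, so no 6.3.5 trigger applies.

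| Case | ALT course (x ULN) | Table 4 | 6.3.5/6.3.6 | 6.2.4.1 text |
|---|---|---|---|---|
| A | 9 to 4 | Restart one level lower (grade 2) | Not met: no cause, not normal | Not met (grade 2) |
| B | 9 to 2 by day 10 | Restart one level lower (grade 1) | Not met: no cause, not normal | Met |
| C | 9 to normal by day 6 | Restart at same dose | Not met: no cause | Met |
| D | 6 to 4 by day 5 | Restart one level lower (grade 2) | No trigger | Not met (grade 2) |

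**Cases A to C** show the main conflict. The peak of 9 exceeds the 8 x ULN trigger, so 6.3.5 applies. Table 4 permits restart in all three, at full dose in C, while the 6.3.5 condition fails in all three.

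**Case D** shows the separate mismatch inside 6.2.4.1. The text sets grade 1 and sends the reader to a table that accepts grade 2. This does not depend on 6.3.5 or on the liver.

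**Sensitivity to baseline.** Inclusion criterion 112 admits AST/ALT up to 3 x ULN. With a baseline of 3 x ULN, the recovery level in 6.3.5 would be met in case B (2 is below 3) but not in case A (4 is above 3). The missing alternative cause still leaves the 6.3.5 condition unmet in both.

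**Search for a precedence rule.** The only routing sentences concern cytokine release. The cross-references do not settle the matter. For rechallenge, 6.3.5 cites 6.3.3, which contains no rechallenge condition, and 6.3.6. Section 6.3.6 relies on 6.2.5 for permanent discontinuation, but 6.2.5 lists no hepatic criterion; those are in 6.3.4.

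**The case against.** The best reply is that the specific rule displaces the general one. Table 4's row is residual, and section 6.3 is devoted to cytokine release, neurologic events and hepatotoxicity. Neurologic events follow the same pattern: Table 5 requires grade 1 where Table 4's residual row would accept grade 2. A careful reader would probably apply 6.3.5 once triggered, and following the strictest rule breaches none of them. This carries weight, and it is why the remedy is a sentence confirming that reading. It does not remove the gap. Where the protocol wants Table 4 displaced for cytokine release, it says so. In 6.3.5, by contrast, "the following rules are recommended for withholding of Amgen investigational products and other protocol required therapies", which is softer than Table 4's direct instructions.

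Two further objections partly stand. Section 6.3.5 says rechallenge may be considered if its condition is met and does not literally say only if; still, it offers no other route. Its opening clause also describes subjects under eligibility criteria requiring normal transaminases, or with underlying liver disease, and this trial admits AST/ALT up to 3 x ULN. That it covers the subjects in the table is therefore an assumption.

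A reader might infer that every grade 3 AST/ALT rise outside cytokine release faces three conflicting conditions. The documents do not support that. Section 6.3.5 applies only after a trigger, which case D does not reach, and DLTs fall under 6.2.5. A reader might also infer that immune-related hepatitis, by counting as an alternative cause, opens AMG 404 rechallenge. Section 6.2.4.2 already sends immune-related events to Appendix G, which stops AMG 404 permanently at grade 3 hepatitis.

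**Conclusion.** The concern holds for clinically significant AST/ALT rises that are not due to cytokine release, are not DLTs and meet a 6.3.5 trigger. For these, Table 4 and sections 6.3.5/6.3.6 give different restart conditions and nothing ranks them. The 6.2.4.1 mismatch, grade 1 or lower against grade 2 or lower, is a separate and more general inconsistency.

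Severity is minor. The documents give no rate for such rises on AMG 596, so the number of subjects affected cannot be estimated, and no effect on an endpoint or analysis is shown. The harm is bounded by sponsor consultation under 6.3.6, close observation above 3 x ULN under Appendix A, the discretion left in 6.3.4 and Table 4's 21-day stop. The conclusion rests on the Appendix G grade bands and on 6.3.5 covering the trial population.

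**What to change.** Add to 6.3.5, and to Table 4 as a footnote like the existing one for cytokine release, that once a 6.3.5 trigger is met AMG 596 and AMG 404 may be restarted only under 6.3.5 and 6.3.6, with Appendix G still applying to AMG 404. This needs a short protocol amendment with ethics committee approval under section 12.1, and no extra visits or data. The downside is that some subjects will be held longer or not restarted.

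Separately, make the 6.2.4.1 text and Table 4 name the same recovery grade for residual grade 3 toxicities. The choice should rest with the sponsor's clinical lead. It changes restart for every toxicity in that row, and Table 3 also uses grade 2 or lower, so grade 1 is not self-evidently the intended value.
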